472 participants' use of ICC services. In addition, biometric data at the post-intervention RDS will be
473 linked with the biometric data from the ICCs to determine utilization. Individual analyses will
474 use descriptive statistics and log-binomial regression to compare the level of each outcome (e.g.,

475 proportion accessing HCT in prior 12 months) by the main exposure of interest (visiting an ICC).
476 We will adjust for individual-level confounders including demographic characteristics. Analyses
477 will use multi-level random effects regression approaches to account for dependence of
478 responses within personal networks [56]. In addition, using the biometric data to link persons
479 between the pre-and post intervention RDS samples, we will conduct exploratory within-
480 individual comparisons of the primary outcome and secondary outcomes. For example,
481 restricting the sample to persons who participated in both the pre- and post intervention RDS
482 samples and are eligible for the outcome, we will compare across control and intervention
483 clusters the proportions of person who transition from not having the outcome to having it and
484 vice versa.

485

486 **Dissemination**

487 This trial represents a public-private partnership and collaboration between investigators
488 at the Johns Hopkins University (Schools of Medicine and Public Health), investigators and
489 research staff at the YR Gaitonde Centre for AIDS Research and Education (YRGCARE), the
490 Targeted Intervention Division of the National AIDS Control Organization, India and several
491 local State AIDS Control Organizations and local non-governmental organizations. Prior to and
492 during the implementation of the trial, quarterly community meetings have been held to keep the
493 community and relevant stakeholders informed on the conduct of the study. Meetings will
494 continue past the end of the trial to inform the communities of the finding. A meeting will also
495 be held with the representatives of the National AIDS control Organization to disseminate the
496 findings. Once the trial is complete, depending on the findings, key stakeholders will decide on
497 whether to adopt the ICC model as a whole or certain aspects of the model as the standard of

498 care. This will require a consideration of the demonstrated effectiveness and cost. If they choose
499 not to adopt the model, clients in sites with ICCs will be transferred back to the relevant
500 government centers and NGOs for services (e.g., ART and OST).

501

502 **DISCUSSION**

503 Dramatic progress has been made in the management and prevention of HIV since the
504 first report in 1981. Yet, key challenges remain. First, implementation strategies need to be
505 identified that can take demonstrated efficacious interventions at an individual level (e.g., ART,
506 OST) and improve their effectiveness in the real-world [37-40, 42]. Second, while ART roll-outs
507 and expanded prevention services have led to overall declines in HIV prevalence across all
508 settings [5], these declines have not been as apparent among key populations such as MSM and
509 PWID [5, 57, 58]. In several countries where HIV epidemics are driven by drug use, HIV
510 prevalence has at best stabilized if not increased over the past decade [5]. Resurgence in reports
511 of both STIs and high-risk behavior have been noted globally among MSM [57]. These two
512 populations are particularly difficult to target because a large majority of them remain hidden
513 and no sampling frame exists making achieving a representative sample challenging. Our trial is
514 unique in its utilization of RDS to evaluate the effectiveness of a community-level intervention
515 in hard to reach populations.

516 Conversations about the end of AIDS and an AIDS-free generation have begun [59, 60].
517 However, for this goal to be realized, prevention, care and treatment services need to reach all
518 populations at risk for HIV infection particularly those that are hardest-to-reach. There is a clear
519 gap in access to services among MSM and PWID. Trials need to be designed to optimize

520 utilization of services in these populations. We believe that this represents one of the first trials
521 aimed at improving the HIV care continuum among MSM and PWID populations.

522
523
524
525
526
527
528
529
530
531
532
533
534
535
536
537
538
539
540

541 **LIST OF ABBREVIATIONS:**

542 Anti-tuberculosis therapy (ATT)
543 Antiretroviral therapy (ART)
544 Directly Observed Therapy (DOT)
545 Focus group discussions (FGD)
546 HIV counseling and testing (HCT)
547 Integrated care centers (ICC)
548 In-depth interviews (IDI)
549 Men who have sex with men (MSM)
550 Needle and syringe exchange programs (NSEP)
551 Non-governmental organizations (NGO)
552 Opioid agonist therapy (OAT)
553 People who inject drugs (PWID)
554 Respondent-driven sampling (RDS)
555 Sexually transmitted infections (STI)
556

557 **ETHICS APPROVAL AND CONSENT TO PARTICIPATE:**

558 This study was approved by the Johns Hopkins and YR Gaitonde Centre for AIDS Research and
559 Education Institutional Review Boards. The reference number for the Johns Hopkins Institutional
560 Review Boards is NA_00047702. With IRB approval, informed consent was obtained verbally,
561 as this study was considered minimal risk.

562

563 **AVAILABILITY OF DATA AND MATERIAL:**

564 This is a protocol paper and so there are no data associated with the paper.

565

566 **COMPETING INTERESTS:**

567 The authors declare that they have no competing interests.

568

569 **CONSENT FOR PUBLICATION:**

570 Not applicable.

571

572 **FUNDING:**

573 This work was supported by the National Institutes of Health, [R01 MH 89266, R01 DA 032059]
574 and the Elton John AIDS Foundation. Additional support was provided by the Johns Hopkins
575 University Center for AIDS Research, the National Institute on Drug Abuse and the National
576 Institute on Allergy and Infectious Diseases [P30 AI094189 and K24 DA035684, T32 AI102623
577 respectively]. The funding bodies did not play a role in design, in the collection, analysis, and
578 interpretation of data; in the writing of the manuscript; and in the decision to submit the
579 manuscript for publication.

580

581 **AUTHOR CONTRIBUTIONS:**

582 [name], [name], [name], [name], [name], [name] and [name] were responsible for the original design of the study and oversee
584 implementation. [name], [name] and [name] contributed to the
585 statistical aspects of the design including randomization, statistical power and proposed analyses.
586 [name] designed all of the data collection systems for the study. All authors read and
587 approved the final manuscript.

588

589 **ACKNOWLEDGEMENTS**

590 We thank [name] for assistance with manuscript preparation and the National AIDS Control
591 Organization (NACO), India, all of our partner non-governmental organizations throughout
592 India, and the countless participants, without whom this research would not have been possible.

593

594 **References**

- 595 1. National AIDS Control Organization. HIV Sentinel Surveillance 2014-15: A Technical Brief. 2015.

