108 awareness of HIV status, reduce injection-related and same-sex risk behavior, improve health,

109 reduce mortality, and decrease the infectiousness of HIV-infected persons in the community
110 through effective viral suppression. We will evaluate the community-level effectiveness of
111 MSM//PWID-focused integrated care centers (ICCs), which will provide core and group-specific
112 HIV prevention and treatment services at a single venue utilizing a cluster-randomized trial
113 design in 22 sites across India.

114

115 Our hypotheses are:

116 1) Establishing ICCs will increase access to HCT and knowledge of HIV status among MSM and
117 PWID.

118 2) In the subset of HIV-infected MSM and PWID, ICCs will increase access to care, use of ART
119 and will decrease community viral load.

120 3) Establishing ICCs will decrease transmission risk behaviors and HIV incidence among MSM
121 and PWID via improved access to prevention services (NSEP, OAT, IEC).

122

123 **METHODS/ DESIGN**

124 **Study design**

125 The study design is a cluster-randomized trial with parallel MSM and PWID strata. ICCs
126 were scaled-up and implemented at sites allocated to the intervention arm, and outcomes will be
127 assessed by pre- and post-intervention surveys at intervention and control sites (**Figure 1**). As
128 MSM and PWID are hidden populations with no sampling frame, respondent-driven sampling
129 (RDS) will be used to accrue samples for the two independent cross-sectional surveys. Sites (10
130 MSM and 12 PWID sites) were randomized in a 1:1 allocation ratio. The trial is currently
131 underway. The pre-intervention survey took place between September 2012 and December 2013;

132 the ICCs were scaled up between June 2014 and February 2015. Post-intervention survey
133 commenced in August 2016 and is expected to be complete by April 2017.

134 **Study sites**

135 Twenty-seven candidate sites were selected (15 PWID, 12 MSM; **Figure 2**) of which 22
136 were included in the trial. Sites were selected to represent regions of India where there was
137 preliminary evidence of high HIV prevalence or high risk of HIV acquisition through discussions
138 with the Targeted Interventions (TI) Division of NACO, India. We ensured sufficient distance
139 between sites to minimize potential overlap (contamination) between intervention and control
140 sites. MSM sites were selected to represent cities with established HIV epidemics among MSM,

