281 First, sites were stratified based on risk group (MSM and PWID) and then additional
282 restriction criteria were used to ensure balance, first within strata and then overall. Within strata,
283 restrictions were made on the basis of geography, HIV prevalence and the primary outcome:
284 HCT in the prior 12 months (**Table 3**). Additional restrictions were made on outcomes among
285 HIV positive persons. All within-strata restrictions were based on RDS-weighted proportions of
286 the outcomes. After strata-specific restrictions were made, the two strata were combined to
287 derive a combined set of allocations. Final restrictions were made using the same outcomes with
288 the exception that both RDS-weighted and unweighted proportions were considered.

289 Restrictions related to geography and HIV prevalence were imposed because both were
290 related to the stage of the HIV epidemic in the target population and HIV service availability.
291 Further, geographic restrictions were important for political reasons, such that all intervention

292 sites were not restricted to one region or state. Additional covariates used in the restriction
293 process represented the primary and secondary outcomes. Of a total 232,848 possible
294 allocations, 596 allocations remained after all restrictions. Across all combinations, there were
295 only two sites that had >75% chance of being randomized to the same arm [53]. Three
296 individuals independent from the study who were blinded to the allocation sequence associated
297 with each of the possible numbers chosen (e.g., 001 to 596) were asked to draw numbered balls
298 from an opaque container to arrive at the final 3 digit number, corresponding to a numbered
299 randomization combination. A recording of the randomization is available at:

300 https://www.youtube.com/watch?v=vmHYHgv_uS0. The final allocation is shown in **Figure 2**.

301

302 *Intervention implementation.*

303 Venue selection. In each intervention site, venues were selected for scale-up following
304 discussions between the State AIDS Control Society, NGO leaders, MSM/PWID community
305 members and study investigators. In all cities, only one site was selected for scale up unless
306 mobility within the city was restricted due to distance or unsafe circumstances, in which case
307 more than one ICC was scaled-up (e.g., Imphal – 3 , Chandigarh – 2, Bilaspur – 2). For the

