391 control clusters of 10-40%, a range of 350-1000 persons in each cluster for HIV-negative
392 outcomes, an RDS design effect of 2, a two-sided α of 0.05, power=0.80 and a within-stratum
393 coefficient of variation ranging from 0.10 to 0.40. We incorporated the RDS design effect
394 (relative to simple random sampling) by doubling the sample size required per cluster after
395 calculating power. For the primary outcome, with 11 intervention and 11 control clusters, we
396 will have 80% power to detect an absolute difference of 12% in the prevalence of the primary
397 outcome in intervention and control clusters (e.g., 42% and 30%, respectively) with a within-
398 stratum coefficient of variation of 0.25 and 1000 participants in each cluster.

399 Our trial was powered to be able to detect differences in the primary outcome, but we
400 also calculated power for secondary outcomes. Power for secondary outcomes that include the
401 full sample (e.g., proportion of PWID reporting sharing injection equipment in the prior 6
402 months) was similar to that for primary outcomes as the methods and the range of outcome
403 prevalence in control clusters was within the range of what was considered for the primary
404 outcome. Power was relatively insensitive to the within-cluster sample size so our ability to
405 detect outcome differences for outcomes where only HIV positive subjects are considered is
406 similar to outcomes where the full RDS sample is used. For outcomes restricted to HIV-positive

407 subjects, we assumed a sample size of 100-300 persons per cluster. Power remained insensitive
408 to the cluster sample size down to a sample size of 100 per cluster. For example, with all other
409 assumptions held constant and an RDS sample size of 150, if the baseline prevalence of the
410 outcome is 30%, we will be able to detect a difference of 14 percentage points (e.g., 30% vs.
411 44%). For outcomes with lower baseline prevalence, we would be able to detect a smaller
412 difference (e.g., if 20% of HIV infected patients are engaged in care in the control sites, we
413 would have adequate power to detect a difference of 9 percentage points [20% vs. 29%]).

414

415 **Analysis plan**

416 *Community level.*

417 The primary analysis will be to compare the prevalence of community-level outcomes
418 across intervention and control clusters, adjusting for pre-intervention prevalence levels. For a

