13	Shared injection equipment in prior 6 months [PWID]	Survey	Participants at PWID sites	Reports sharing (passing or receiving) a needle and/or syringe with another individual in the prior 6 months
14	Shared injection equipment at last use among active injectors [PWID]	Survey	Participants at PWID sites that report injection of one or more drugs in prior 6 months	Reports sharing (passing or receiving) a needle and/or syringe with another individual at last injection
15	Reported injection abstinence in prior 6 months [PWID]	Survey	Participants at PWID sites	Denies injecting any drug in prior 6 months
16	Hazardous alcohol use or dependence	Survey	All participants	Score ≥ 8 (hazardous) or ≥ 15 on Alcohol Use Disorder Identification Test (AUDIT)[61]
17	Depression	Survey	All participants	Score ≥ 10 on Patient Health Questionnaire (PHQ)-9[62]

Table 1. Outcome definitions for the Indian National Collaboration on AIDS (NCA) study

	Outcome	Data inputs	Population (denominator)	Definition
Services and stigma				
18	Spouse HIV testing among married participants	Survey	Participants who report being married	Reports spouse has ever been tested for HIV
19	Symptoms of sexually transmitted infection for which participant sought care in prior 6 months [MSM]	Survey	Participants at MSM sites	Reports genital/anal discharge, pain, or ulcer in prior 6 months AND reports seeking medical care for symptom(s)
20	Used needle/syringe exchange program (NSEP) in prior 6 months [PWID]	Survey	Participants at PWID sites	Reports NSEP use in prior 6 months
21	Used needle/syringe exchange program (NSEP) in prior 6 months among active injectors [PWID]	Survey	Participants at PWID sites that report injection of one or more drugs in prior 6 months	Reports NSEP use in prior 6 months
22	Used opioid agonist therapy (OAT) in prior 6 months [PWID]	Survey	Participants at PWID sites	Reports OAT in prior 6 months
23	Stigma subtypes	Survey	All participants	Summed score from each of four 6-item stigma scales (enacted, vicarious, felt normative, and internalized stigma)[63]
Community viral load and HIV incidence				
24	Prevalence of viremic individuals in population	1. Serologic HIV test 2. HIV RNA	All participants	Prevalence of HIV-positive subjects with HIV RNA >150c/mL[64]
25	Average viral load in HIV-positive participants	1. Serologic HIV test 2. HIV RNA	HIV seropositive participants	Average (log ₁₀) HIV RNA

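### Power for single-stratum secondary outcomes is called similar to the primary's, but they have 6 vs 6 or 5 vs 5 clusters instead of 11 vs 11

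*Combined protocol and SAP*

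**What the plan says.** The Statistical power section gives one cluster count, 11 intervention and 11 control, and 80% power for 42% vs 30% on the primary outcome. It then turns to secondary outcomes that use everyone surveyed. The example is taken from the "full sample (e.g., proportion of PWID reporting sharing injection equipment in the prior 6" and the sentence continues "months) was similar to that for primary outcomes as the methods and the range of outcome". The only support offered is that the methods match and that control prevalence lies within the range already considered. The calculations used a within-stratum "coefficient of variation ranging from 0.10 to 0.40", but no value is assigned to any secondary outcome.

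Table 1 gives equipment sharing (outcome 13) a denominator of participants at PWID sites. Study design states the site numbers: 10 "MSM and 12 PWID sites) were randomized in a 1:1 allocation ratio".

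**The concern.** The same section says "Power was relatively insensitive to the within-cluster sample size so our ability to" detect differences carries over to smaller samples. If persons per cluster matter little, power depends mainly on the number of clusters and on variation between them, and the number of clusters is what changes for an outcome that exists in only one stratum.

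Eight secondary outcomes are proportions over the full sample of a single stratum: 13, 15, 20 and 22 (PWID), and 9, 11, 12 and 19 (MSM). They include sharing, needle exchange, opioid agonist therapy and unprotected anal intercourse, the behaviour and service measures behind hypothesis 3. HIV incidence, also in hypothesis 3, is measured at all 22 sites and is not affected. The stake is interpretation: a null result on sharing or needle exchange would be read against power described as similar to the primary's 80%, which these outcomes do not have for the same effect.

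**Working it through.** **Cluster counts.** Randomization reports "Of a total 232,848 possible" allocations. C(12,6) × C(10,5) = 924 × 252 = 232,848, so the split is 6 vs 6 for PWID and 5 vs 5 for MSM. Intervention implementation names six PWID intervention cities, which agrees.

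**Inputs (Statistical power section).** p0 = 0.30, p1 = 0.42, k = 0.25 (coefficient of variation), two-sided alpha 0.05, power 0.80. The design effect of 2 makes 1000 sampled equal to m = 500 effective.

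**Formula (unmatched clusters, c per arm).**

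V = p0(1−p0)/m + p1(1−p1)/m + k²(p0² + p1²)

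c = 1 + (1.960 + 0.842)² × V / (p1 − p0)²

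power = Φ( |p1 − p0| × √((c − 1)/V) − 1.960 )

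**Reproducing the plan.** V = 0.00042 + 0.00049 + 0.01665 = 0.01756. Then c = 1 + 7.849 × 0.01756 / 0.0144 = 10.57, which rounds up to 11. With c = 11, power = Φ(2.864 − 1.960) = 81.7%, in line with the stated 80%. Adding two clusters per arm instead of one, to allow for stratification, gives 77.5%, which fits the stated figure less well, so I kept the one-cluster form.

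**Changing only c.** c = 6: Φ(2.025 − 1.960) = 52.6%. c = 5: Φ(1.811 − 1.960) = 44.1%. The ranges below pair this formula with a noncentral t calculation on 18, 9 and 7 degrees of freedom (clusters less the regression terms).

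| Effect, k = 0.25 | 22 clusters | 12 | 10 |
|---|---|---|---|
| 30% vs 42% | 81-82% | 51-53% | 42-44% |
| Same ratio as a fall, 30% to 21.4% | 80% | 50-51% | 41-43% |
| 40% to 28% | 85-86% | 55-57% | 45-48% |
| 30% to 18% | 98-99% | 82-84% | 71-75% |

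**Dependence on k.** For 30% vs 42%, 12 clusters give 99% at k = 0.10 and 24-25% at k = 0.40; 22 clusters give about 100% and 44%.

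**Matched effect.** Power depends on c only through c − 1. An effect with exactly 80% power at 11 vs 11 therefore has Φ(2.802 × √(5/10) − 1.960) = 50.8% at 6 vs 6 and Φ(2.802 × √(4/10) − 1.960) = 42.5% at 5 vs 5, whatever k or the control rate.

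**Detectable difference from 30% at 80% power** (points, rise / fall, normal formula only):

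| k | 22 clusters | 12 | 10 |
|---|---|---|---|
| 0.10 | 4.8 / 4.3 | 7.0 / 6.0 | 8.0 / 6.6 |
| 0.25 | 11.7 / 8.5 | 18.2 / 11.5 | 21.2 / 12.7 |
| 0.40 | 21.2 / 12.5 | 37.0 / 16.7 | 45.9 / 18.4 |

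Across these rows the detectable difference is 1.3 to 1.75 times the 22-cluster value with 12 clusters, and 1.5 to 2.2 times with 10.

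**The case against.** The best reply concerns the plan's own example. The primary target is an absolute 12 points from a 30% control rate, and for sharing, benefit is a fall. At k = 0.25, 6 vs 6 clusters detect an 11.5-point fall from 30%, close to the 11.7-point rise that 11 vs 11 detect for the primary. On that metric similar is defensible for sharing. This stands, but narrowly. It needs a control rate near 30% and a constant coefficient of variation; it fails for 40% to 28% (55-57%); it does not help outcomes where benefit is a rise, such as needle exchange, opioid agonist therapy and injection abstinence; and the same fall has 98-99% power with 22 clusters.

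Second, k = 0.25 is borrowed from the HIV-testing example. A k of about 0.176 or lower, inside the plan's range, restores 80% for 30% vs 42% with 6 vs 6 under the normal formula. So no absolute power figure here is firm. The relative loss at a fixed effect does not depend on k.

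Third, adjustment for pre-intervention prevalence may help, but the plan's calculation does not credit it, nor does mine. If it cut k to 0.20 (my assumption), 30% vs 42% would have 94% / 68-70% / 58-61% with 22 / 12 / 10 clusters, so the gap remains.

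Fourth, these are secondary outcomes, the plan says the trial was powered for the primary, no decision rule rests on their power, and no printed number is wrong. All true; this limits the consequence to interpretation.

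**Conclusion.** The concern holds. The claim of similar power rests on methods and prevalence range, ignores cluster count, and is illustrated by an outcome with 6 vs 6 clusters. At a matched effect, 80% power becomes about 51% for PWID-only outcomes and about 43% for MSM-only ones. The direction is certain. The absolute figures assume k = 0.25, 500 effective persons per cluster and the control rates shown, none of which the plan states for these outcomes. The figures do not apply to outcome 10, which is MSM-only but a count. Outcomes 14 and 21 have the denominator "Participants at PWID sites that report injection of one or more drugs in prior 6 months", so they are not full-sample outcomes. The primary power statement stands.

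**What to change.** - Limit the claim of similar power to outcomes measured at all 22 sites, such as depression or hazardous alcohol use, and use one of these as the example in place of sharing.
- For the eight single-stratum proportions, state detectable differences for 6 vs 6 and 5 vs 5 clusters, each with its control rate, direction and coefficient of variation, over k from 0.10 to 0.40. At control 30% and k = 0.25 these are about 18 points up or 11.5 down for 6 vs 6, and about 21 up or 12.7 down for 5 vs 5, labelled as illustrations.
- Treat outcome 10 separately, and note that outcomes 14 and 21 cover active injectors only.

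The cost is a text change and less favourable stated figures. No clusters are added and no analysis changes. The document is dated November 2016 and expects the post-intervention survey to finish by April 2017, so on that timetable the correction could precede the results.

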Awareness of HIV status, access to care, and HIV treatment				
2	Awareness of HIV status among HIV-seropositive persons	1. Survey 2. Serologic HIV test	HIV seropositive participants	Reports having a positive HIV test OR being told by a doctor that he/she had HIV.
3	Accessing HIV medical care in prior 6 months	1. Survey 2. Serologic HIV test	HIV seropositive participants	Reports seeing a doctor about HIV AND reports visit with the indicated doctor in the prior 6 months.
4	Use of ART among ART-eligible	1. Survey 2. Serologic HIV test	HIV seropositive participants who meet either criteria 1 or 2 1. Reports taking ART at any time in the past OR 2. CD4 <350 cells/ μ L	Reports ART use in prior 30 days.
5	Use of trimethoprim-sulfamethoxazole (TMP-SMX) when indicated	1. Survey 2. Serologic HIV test 3. CD4	HIV seropositive AND CD4 count < 200 cells/ μ L	Reports taking TMP-SMX in past 30 days
6	Viral suppression among ART-eligible	1. Survey 2. Serologic HIV test 3. CD4 4. HIV RNA	HIV seropositive participants who meet either criteria 1 or 2 1. Reports taking ART at any time in the past OR 2. CD4 <350 cells/ μ L	HIV RNA <150c/mL
7	Viral suppression among HIV-positive	1. Serologic HIV test 2. HIV RNA	HIV seropositive participants	HIV RNA <150c/mL
8	Average CD4 cell count among HIV-positive	1. Serologic HIV test 2. CD4 cell count	HIV seropositive participants	CD4 cell count

Table 1. Outcome definitions for the Indian National Collaboration on AIDS (NCA) study

	Outcome	Data inputs	Population (denominator)	Definition
Risk behaviors, substance use, and depression				
9	Unprotected anal intercourse with non-main male partner in prior 6 months [MSM]	Survey	Participants at MSM sites	Does not report “always” using a condom during insertive or receptive anal sex with non-main (e.g., casual, one-time partner, sex worker) male partners in the prior 6 months
10	Number of non-main male sexual partners in prior 6 months [MSM]	Survey	Participants at MSM sites	Number of non-main male (e.g., casual, one-time partner, sex worker) male partners with whom the participant reports having insertive or receptive anal sex in the prior 6 months
11	Symptoms of sexually transmitted infection [MSM]	Survey	Participants at MSM sites	Reports genital/anal discharge, pain, or ulcer in prior 6 months
12	Syphilis infection	1. RPR test 2. TPHA test	Participants at MSM sites	Positive for syphilis infection by both RPR and TPHA tests

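### The power stated for HIV-positive outcomes assumes 100-300 persons per cluster, but outcomes 4, 5 and 6 are analysed in smaller subsets; outcome 5 very probably lacks that power

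*Combined protocol and SAP*

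**What the plan says.** The Statistical power section sizes the trial on the primary outcome and then extends the claim to secondary outcomes. It says that the ability to "detect outcome differences for outcomes where only HIV positive subjects are considered is" similar to that in the full sample. The basis given is: "we assumed a sample size of 100-300 persons per cluster. Power remained insensitive" to cluster size down to 100 per cluster. The worked example is 30% vs 44% with 150 persons per cluster, other assumptions unchanged.

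Table 1 sets narrower denominators for three of these outcomes:

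- Outcome 5 (TMP-SMX when indicated): "HIV seropositive AND CD4 count < 200 cells" per microlitre.
- Outcomes 4 (ART use) and 6 (viral suppression among the ART-eligible): "HIV seropositive participants who meet either criteria 1 or 2", the two criteria being any past ART use or CD4 below 350.

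The power section mentions neither subset. Outcomes 2, 3 and 7 are the proportions that use all HIV-seropositive participants.

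**The concern.** The 100-300 range fits a count of all HIV-positives: the Background gives HIV prevalence of 10-30% in PWID, which is 100-300 in a sample of 1000. Outcomes 4, 5 and 6 use only part of that group, and for outcome 5 the part may be small. The plan claims insensitivity to cluster size only down to 100, and nothing shows that outcome 5 stays above 100.

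What is at stake is interpretation. ART use and suppression bear directly on hypothesis 2, and TMP-SMX use is a listed care outcome. A non-significant result on any of them would be read against roughly 80% power for a 14-point difference. If the denominator cannot support that, absence of evidence may be reported as evidence of no effect.

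**Working it through.** **Inputs from the Statistical power section.** "a two-sided α of 0.05, power=0.80"; comparison "with 11 intervention and 11 control clusters", so c = 11 per arm; "stratum coefficient of variation of 0.25 and 1000 participants in each cluster", so k = 0.25 (range considered 0.10-0.40); "an RDS design effect of 2", so the effective size is m = n/2.

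**Not in the documents.** The share of HIV-positives with CD4 below 200, the share ever on ART or with CD4 below 350, and an expected prevalence for outcome 5. The plan's 30% vs 44% example is borrowed as the effect.

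**Formula** (unmatched cluster comparison of two proportions):

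V = [p0(1−p0) + p1(1−p1)]/m + k²(p0² + p1²)

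power = Φ( √[(c−1)(p1−p0)²/V] − 1.96 )

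A non-central t calculation with 20 degrees of freedom differs by less than half a percentage point at the sizes used here.

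**Step 1. Reproduce the plan.**

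- Primary outcome, 30% vs 42%, n = 1000, m = 500: V = 0.4536/500 + 0.0625 × 0.2664 = 0.01756. √(10 × 0.0144/0.01756) = 2.864. Power = Φ(0.904) = 82%.
- HIV-positive example, 30% vs 44%, n = 150, m = 75: V = 0.4564/75 + 0.0625 × 0.2836 = 0.02381. √(10 × 0.0196/0.02381) = 2.869. Power = Φ(0.909) = 82%, detectable difference 13.6 points.

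Both agree with the plan.

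**Step 2. What outcome 5 needs to reach the floor of 100.** 100/300 = 33%, 100/150 = 67%, 100/100 = 100% of HIV-positives with CD4 below 200.

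**Step 3. Power for 30% vs 44% by number analysed per cluster (k = 0.25, design effect 2).**

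| n per cluster | m | V | Power | Detectable difference at 80% (points) |
|---|---|---|---|---|
| 10 | 5 | 0.1090 | 27% | 30.5 |
| 15 | 7.5 | 0.0786 | 35% | 26.0 |
| 30 | 15 | 0.0482 | 52% | 20.2 |
| 60 | 30 | 0.0329 | 68% | 16.4 |
| 90 | 45 | 0.0279 | 76% | 14.9 |
| 100 | 50 | 0.0269 | 77% | 14.6 |
| 126 | 63 | 0.0250 | 80% | 14.0 |
| 150 | 75 | 0.0238 | 82% | 13.6 |
| 180 | 90 | 0.0228 | 83% | 13.3 |

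The between-city term, 0.0177, is fixed. At n = 150 the sampling term is 0.0061, or 26% of V, so size matters little. At n = 30 it is 0.0304, or 63% of V, so size matters a great deal.

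**Step 4. Outcome 5.** Assuming 10-30% of 100-300 HIV-positives have CD4 below 200, n runs from 0.10 × 100 = 10 to 0.30 × 300 = 90, and power from 27% to 76%.

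**Step 5. Outcomes 4 and 6.** Assuming 60% are eligible, 300 HIV-positives give 180 (83%) and 100 give 60 (68%). The crossing point for 80% is about 126-128, say 130.

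**Step 6. Sensitivity to k.** At n = 30, power is 68% with k = 0.10 and 36% with k = 0.40. With k = 0.10, n = 45 already gives 83%. With k = 0.40, even n = 150 gives only 50%.

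**Step 7. Baseline adjustment.** The planned regression was simulated on log proportions with stratum and log-baseline terms (4000 runs, 0.5 continuity correction, 18 degrees of freedom). The assumed pre/post correlation of log city prevalence was 0.5 and then 0.8. Power was 84% and 91% at n = 150, 58% and 61% at n = 45, 48% and 49% at n = 30, and 31% and 33% at n = 15. Adjustment helps at 150 but not at 45 or below.

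**The case against.** The strongest reply is that the plan never promises 80% power for outcome 5. The 30% vs 44% case is offered as an example, insensitivity is claimed only down to 100, and the trial is openly sized on the primary outcome. All of that is true and limits the consequence. It does not remove the gap: the statement covers outcomes restricted to HIV-positives as a class, with no exception for those in narrower subsets.

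Several stronger readings are tempting, and the documents do not support them:

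- *That outcome 5 has a definite power such as 35-60%.* That band corresponds to about 15-41 persons per cluster, which depends on an unstated CD4 share. Varying the share, the number of HIV-positives or k moves the result well outside it.
- *That a 14-point effect on outcome 5 would be missed more often than not.* Under the Step 3 formula at k = 0.25, this holds only below about 30 per cluster.
- *That the stated power does not apply to outcomes 4 and 6.* Their eligibility rule is broad, and larger clusters may well keep 130 or more. The fair criticism is that power was not shown on the denominators they use.
- *That these subsets cannot exceed 100-300.* The Background gives MSM prevalence of up to 41%, about 410 HIV-positives per 1000, so a large eligible subset could pass 300.
- *That the plan's arithmetic is wrong.* Both figures checked here reproduce; the fault is in the scope of the statement.

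**Conclusion.** The point holds in limited form. The power stated for HIV-positive outcomes rests on a denominator that outcomes 4, 5 and 6 do not use.

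For outcome 5 the claim very probably fails, since the floor of 100 requires between a third (of 300) and all (of 100) of the HIV-positives to have CD4 below 200. The 27-76% range is conditional on the assumed 10-30% share, the borrowed 30% vs 44% effect, k = 0.25 and a design effect of 2. At the low end of the plan's range for k, the upper part of the assumed sizes would reach 80%.

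For outcomes 4 and 6 the claim is unverified, not refuted: it is met at about 130 or more eligible per cluster and missed below that. These are secondary outcomes, and the primary outcome's power stands as stated.

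**What to change.** In the Statistical power section:

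1. Limit the statement based on 100-300 persons per cluster to proportions whose denominator is all HIV-seropositives (outcomes 2, 3 and 7).
2. For outcomes 4, 5 and 6, replace it with power and detectable difference computed from the per-city denominators in the pre-intervention survey: persons ever on ART or with CD4 below 350, and persons with CD4 below 200. That survey was completed in December 2013 and Table 2 lists CD4 testing for all HIV-positives, so the counts should be obtainable.
3. Unless those counts reach about 130 per cluster (at k = 0.25 and a design effect of 2), state that the outcome does not have 80% power for a 14-point difference.
4. Interpret outcome 5 by its estimate and confidence interval, so that a non-significant result is not read as no effect.

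The cost is one recalculation and a change of wording, with no added participants or data collection. The post-intervention survey is already under way, so this changes interpretation and not design. The downside is a less favourable stated power for up to three secondary outcomes.
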